PALACE 1, PALACE 2, and PALACE 3: The efficacy and safety of apremilast for the treatment of psoriatic arthritis was evaluated in 3 multi-center, randomized, double blind, placebo controlled studies of similar design. A total of 1493 adult patients with active psoriatic arthritis (PsA) (\geq 3 swollen joints and \geq 3 tender joints) despite prior or current treatment with disease-modifying antirheumatic drug (DMARD) therapy were randomized to placebo (n=496), apremilast 20 mg (n=500), or apremilast 30 mg (n-497) given orally twice daily. Patients were allowed to receive concurrent DMARD therapy. The primary endpoint, the percentage of patients achieving American College of Rheumatology (ACR) 20 response at week 16, was achieved by 38%, 32% and 41% of patients taking apremilast 30 mg twice daily +/- DMARDs in PsA-1, PsA-2, and PsA-3, respectively, with only 18-19% of patients on placebo +/- DMARDs resulted in greater improvement in psoriatic arthritis symptoms and was associated with a favorable safety profile. The most common adverse reactions leading to discontinuation for patients taking OTEZLA were nausea (1.8%), diarrhea (1.8%), and headache (1.2%).⁷

A Pilot Study of an Oral Phosphodiesterase Inhibitor (Apremilast) for Atopic Dermatitis in Adults): this open-label study tested the effects of apremilast 20 mg BID (APR20) and apremilast 30 mg BID (APR 30) in sixteen adults with atopic dermatitis. After three months, the group receiving APR20 had significant reductions in pruritus and the Dermatology Life Quality Index (DLQI), but not in the Eczema Area and Severity Index (EASI). The APR30 group had significant reductions in the EASI and DLQI.⁴

A. Objectives:

Efficacy Endpoints:

- a. Primary Endpoint Measures:
 - i. Proportion of patients who achieve an Investigator's Global Assessment (IGA) score of 0 (clear) or 1 (almost clear) at Week 16. Clinical improvement in a patient's eczematous lesions corresponds with a decrease in IGA, and a score of 0 (clear) or 1 (almost clear) is considered a significant clinical response.
- b. Secondary Outcome Measures
 - i. Proportion/percentage of subjects achieving BSA < 3%
 - ii. Mean and percentage change from baseline in percent of BSA involvement
 - iii. Mean and percent change of the Dermatology Life Quality Index (DLQI) from baseline
 - iv. Mean and percentage change from baseline in itch on Numerical Rating Scale (NRS) pruritus scale

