 - v. Mean and percentage change from baseline in Eczema Area and Severity Index (EASI) score at week 16

Safety Endpoints:

Safety and tolerability will be evaluated according to the frequency and severity of adverse events and changes in physical examinations or vital signs.

II. Research Plan

A. Overall Study Design:

Open label phase 2 investigational study of efficacy and safety of apremilast 30 mg BID in chronic atopic dermatitis when added to the FDA approved treatment dupilumab for atopic dermatitis that is not providing adequate clinical responses. The study will have 1 phase:

• Open label treatment period apremilast 30 mg BID

Following informed consent, subjects will be screened on the basis of atopic dermatitis severity and inadequate treatment response to current therapies. IGA, BSA, pruritus NRS, EASI, complete physical examination, medical history, and concomitant medications will be reviewed. Eligible subjects will be administered treatment with apremilast 30 mg BID while continuing their prior inadequate atopic dermatitis treatment regimen. During the treatment phase, study drug will be provided in an oral form and will be titrated over 5 days and then taken twice daily thereafter. Subjects return to clinic for reevaluation. Efficacy endpoints will be assessed at weeks 2, 4, 8, 16, and 24. Week 16 is the last week of study drug dispensation. Efficacy and safety indices will be assessed as per the Schedule of Assessments.

Treatment Assignment and Randomization

No randomization will be used, as this is an open label study. There will be no blinding and investigators will have knowledge of the treatment each subject is administered.

All patients seen in the Tufts Dermatology Clinic during the enrollment period who are not currently responding to existing FDA approved atopic dermatitis therapy and thus have not achieved a IGA of 0 or 1 at screening, and meet all other inclusion/exclusion criteria, will be offered participation in the study.

B. Statistical methods:

Sample size: We will screen up to 20 patients to ensure that 16 patients complete the study.

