General statistical Methods: A clinical response to apremilast for the purposes of this study will be defined as an Investigator Global Assessment score of 0 (clear) or 1 (almost clear). The end points of the study will be assessed at Week 16. A period of 16 weeks was chosen, as this was the time frame utilized for primary endpoint reporting in the ESTEEM clinical program.^{6,8} An additional 8 weeks of study drug will be provided to assess enhanced clinical benefit with continued use at 24 weeks. A rate of incompletion and/or drop out of subjects has been factored in to assure great than 16 patients will complete the study.

The analysis will be primarily descriptive. Mean, standard deviation, median, minimum, maximum, and 95% confidence interval for mean will be provided for continuous variables. Changes and percent changes from pre-treatment to on-treatment time points will be calculated for continuous efficacy points. Graphical displays of changes over time may be presented for key outcomes. Counts, percentages, and 95% confidence intervals will be provided for categorical variables. Subgroup analyses, such as gender stratification and stratification based on baseline treatment regimens, will be performed to identify a patient population that achieves the most benefit.

Efficacy analyses will only use data from participants who complete at least 16 weeks of study treatment in order to evaluate the primary endpoint.

Efficacy:

Primary Endpoint

Patients' Investigator's Global Assessment $(IGA)^9$ will be assessed at weeks 2, 4, 8, 16, and 24, with the primary endpoint being the proportion of patients with an IGA of 0 (clear) or 1 (almost clear) at Week 16.

Secondary Endpoints

Secondary endpoints will be assessed according to the scale of the outcome variable of interest. BSA and Eczema Area and Severity Index¹⁰ will be assessed along with IGA at all study visits. For quality of life outcomes, the Dermatology Life Quality Index (DLQI)¹¹ will be used to assess changes from baseline in overall score will be provided. Assessment of outcomes of each protocol-scheduled time point (Weeks 2, 4, 8, 16, and 24) will be performed for each endpoint. Various schemes will be assessed for missing data imputation if needed. The change in the patient's Numerical Rating Scale for Pruritus (NRS) will be assessed.¹²

Background and demographic characteristics:

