Subjects' age, weight, height and other continuous demographic and baseline characteristics will be summarized using descriptive statistics (mean, standard deviation, minimum and maximum), while gender, race and other categorical variables will be summarized with frequency tabulations. Medical history data will be summarized using frequency tabulations. Individual subject listings will be provided. A table of baseline demographic information of subjects who received study medication and controls will be provided for comparison between the two groups.

Safety:

Safety Primary Endpoints

The safety analysis will be descriptive in nature. All subjects who take at least 1 dose of the study medication will be included in the safety analyses. Safety and tolerability will be evaluated by tabulations of adverse events, which will be recorded from the time the subject signs informed consent. Adverse events will be classified on the basis of Common Terminology Criteria for Adverse Events (CTACAE) coding and summarized for each treatment. Adverse events will be summarized by system organ class, preferred term, relationship to study drug, and severity. Serious AEs and AEs leading to death or resulting in premature discontinuation will be tabulated and listed separately. Study medication-related AEs will be listed separately. Drop-out rate and reasons for early termination will be reviewed and tabulated.

Prior and concomitant medications will be reviewed and tabulated by treatment. Physical examination changes and vital signs including weight will be assessed for potential clinical significance; changes from pre-treatment to on-treatment time points will be tabulated for continuous parameters; as warranted.

Assessment of flare of atopic dermatitis will be summarized descriptively.

C. Subject Characteristics

Inclusion criteria:

- 1. Signed and dated informed consent indicating the subject has been informed of all aspects of the study
 - D. Non-English speakers may be enrolled in the study in accordance with the IRB's short form policy.

- 2. Subject is willing and able to comply with treatment plan, study drug administration, and study protocol requirements
- 3. Male or females of any ethnic origin or race at least 18 years of age at time of informed consent
- 4. Subject has a documented clinical diagnosis of chronic atopic dermatitis for at least 6 months prior to screening visit and is a candidate for systemic therapy

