- 5. Subjects must fulfill criteria outlined in the following clinical categories:
 - Subjects must be currently using and experiencing an inadequate response to dupilumab which is FDA approved for the treatment of moderate to severe atopic dermatitis. An inadequate response is defined as an IGA of 2 or more.
 - At the time of screening, subject must have a partial or inadequate response to their current treatment regimen. A partial or inadequate response at screening is defined as having both of the following:
 - Not having achieved an Investigator's Global Assessment score of 0 (clear) or 1 (almost clear).
 - Subjects must be on dupilumab for at least 12 weeks and willing to continue on dupilumab on a stable dose (40 mg weekly or every other week) while also receiving the study drug
- 6. Females of childbearing potential (FCBP) must have a negative pregnancy test at Screening and Baseline. While on investigational product and for at least 28 days after taking the last dose of investigational product, FCBP who engage in activity in which conception is possible must use one of the approved contraceptive options described below:

Option 1: Any one of the following highly effective methods: hormonal contraception (oral, injection, implant, transdermal patch, vaginal ring); intrauterine device (IUD); tubal ligation; or partner's vasectomy;

OR

Option 2: Male or female condom (latex condom or nonlatex condom NOT made out of natural [animal] membrane [for example, polyurethane]; PLUS one additional barrier method: (a) diaphragm with spermicide; (b) cervical cap with spermicide; or (c) contraceptive sponge with spermicide.

- 7. Male subjects (including those who have had a vasectomy) who engage in activity in which conception is possible must use barrier contraception (male latex condom or non-latex condom NOT made out of natural [animal] membrane [for example, polyurethane]) while on study medication and for at least 28 days after the last dose of study medication
- 8. If receiving concomitant medications for any reason, must be on a stable regimen and willing to stay on a stable regimen. This includes emollients, which should stay stable throughout the study.

Exclusion criteria:

- 1. Prior hypersensitivity reaction or exposure to apremilast

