	Basenne	± 3 days	3 days	± 3 days	10 ± 3 days	24 ± 3 days	nation
Informed Consent	Х	uujs		duyb	auyo	duyb	
Atopic Dermatitis diagnosis, medical history	Х						
Concomitant/prio r Medications	Х	Х	X	X	X	X	Х
Complete physical examination ²	Х						Х
Targeted physical examination ³		Х	Х	Х	X	Х	
Vital signs (Temperature, resting pulse, seated blood pressure)	Х	x	X	Х	Х	Х	Х
Demographic information ⁴	Х						
CLINICAL EVALUATION							
Assessment of atopic dermatitis ⁵	Х						
Investigator's Global Assessment of disease (IGA)	Х	X	Х	Х	Х	Х	Х
Body Surface Areas (BSA)	Х	Х	X	X	X	X	Х
NRS Pruritus scale	Х	Х	Х	Х	Х	X	Х
Eczema Area and Severity Index (EASI)	Х	Х	Х	Х	Х	Х	Х
Photography	Х	Х	Х	Х	Х	Х	Х
PATIENT REPORTED OUTCOMES							
Dermatology Life Quality Index (DLQI)	Х	X	Х	Х	X	Х	Х
OTHER ACTIVITIES							
Study Drug Dispensing	Х		X	X	X		
Drug Accountability		Х	X	X	Х	X	Х
Adverse Event Reporting		Х	X	X	X	X	Х
Review concomitant medications	Х	X	Х	Х	X	Х	Х
Urine pregnancy test ⁶	Х	X	Х	Х	Х		

¹Baseline visits may occur at the same time as the screening visit, or within 4 weeks of the screening visit.

²Complete physical examination includes weight, general appearance, skin, HEENT (head, eyes, ears, nose, throat), heart, lungs, abdomen, lower extremities, neurologic and lymph nodes. Height will be recorded at screening only.

³ Targeted physical examination consists of weight, examination of heart, lungs, abdomen, lymph nodes, and lower extremities, as well as any area of patient-reported AEs.

⁴ Demographic information including but not limited to age, race, gender, ethnicity

⁵ For study eligibility, subjects must have active atopic dermatitis at Screening, which has been diagnosed or confirmed by a dermatologist.

⁶ Urine pregnancy test (human chorionic gonadotropin; HCG) is required only for women of child-bearing potential

Assessments of Efficacy:

- Investigators Global Assessment (IGA)
- **Body surface area** (BSA) of involved skin will be measured at Screening, Baseline, and at following visits according to the Schedule of Assessments until study completion.
- Numerical Rating Scale (NRS) Pruritus Scale
- EASI
- DLQI

Assessments of Health-Related Quality of Life:

- Dermatology Life Quality Index will be assessed by the subject at Day 1, and Weeks 2, 4 8,

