The Investigator's Global Assessment of atopic dermatitis is scored on a 5-point scale (0-4), reflecting a global consideration of the erythema, inducation and scaling. The clinical evaluator of atopic dermatitis will perform an assessment of the overall severity of atopic dermatitis and assign an IGA score and category as described in Table 3. The assessment will be a static evaluation without regard to the score at a previous visit.

Score	Category	Description*
0	Clear	Atopic dermatitis is cleared, except for any residual discoloration (post-inflammatory hyperpigmentation and/or hypopigmentation).
1	Almost Clear	Overall, the atopic dermatitis is not entirely cleared and remaining lesions are light pink (not including post inflammatory hyperpigmentation) and/or; have barely palpable hard thickened skin and/or papules and/or; have barely perceptible lichenification; excoriation and oozing/crusting are absent.
2	Mild	Overall, the atopic dermatitis consists of lesions that are light red; with slight, but definite hard thickened skin and/or papules; with slight, but definite linear or picked scratch marks or penetrating surface injury; with slight, but definite thickened skin, fine skin markings, and lichenoid scale; oozing/crusting is absent.
3	Moderate	Overall, the atopic dermatitis consists of lesions that are red; with easily palpable moderate hard thickened skin and/or papules; with moderate linear or picked scratch marks or penetrating surface injury; with moderate thickened skin, coarse skin markings, and coarse lichenoid scale; with slight oozing/crusting.
4	Severe	Overall, the atopic dermatitis consists of lesions that are deep, dark red; with severe hard thickened skin and/or papules; with severe linear or picked scratch marks or penetrating surface injury; with severe thickened skin with very coarse skin markings and lichenoid scale; with moderate to severe oozing/crusting.

Table 3. Investigator's Global Assessment (IGA) Score

* The IGA will exclude scalp, palms, and soles from the assessment/scoring.

EASI

Score		Description
Ery	thema (E)	
0	Absent	None; may have residual discoloration (post-inflammatory hyperpigmentation and/or hypopigmentation)
1	Mild	Light pink to light red
2	Moderate	Red
3	Severe	Deep, dark red
Ind	uration/Papulatio	n (İ)
0	Absent	None
1	Mild	Barely palpable to slight, but definite hard thickened skin and/or papules
2	Moderate	Easily palpable moderate hard thickened skin and/or papules

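### The BSA < 3% secondary endpoint has no baseline condition, so a subject already below 3% who does not change counts as a success

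*Protocol*

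**What the plan says.** Protocol, A. Objectives, gives the first secondary outcome as "Proportion/percentage of subjects achieving BSA < 3" (in percent). The wording contains no baseline condition and no denominator. The other four secondary outcomes are all changes from baseline.

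Protocol, B. Statistical methods, sets Week 16 as the time of assessment and supplies the only efficacy denominator, which the SAP repeats: "Efficacy analyses will only use data from participants who complete at least 16 weeks of study treatment". It also says how a proportion is to be reported: "Counts, percentages, and 95% confidence intervals will be provided for categorical variables".

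On entry, Protocol, C. Subject Characteristics, inclusion criterion 5, sets one numeric severity rule: "An inadequate response is defined as an IGA of 2 or more". BSA is looked at during screening (Overall Study Design: "IGA, BSA, pruritus NRS, EASI, complete physical examination, medical history, and concomitant medications will be reviewed"), but no threshold is attached to it there or in any inclusion or exclusion criterion. The IGA section describes that scale as "reflecting a global consideration of the erythema, inducation and scaling".

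**The concern.** The stated aim is to move patients from an inadequate response on dupilumab to an adequate one by adding apremilast. In a single-arm study the pre-treatment state is the only comparator, so a responder endpoint serves that aim only if a responder has to have changed.

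The primary endpoint largely meets this condition: IGA 0 or 1 is excluded at screening, so an IGA responder at Week 16 has moved since then. The BSA endpoint has no matching rule. IGA 2, labelled mild, is eligible, and its descriptors cover colour, thickening, scratch marks, lichenification and oozing, not the area involved. Every entrant has also had at least 12 weeks of dupilumab, so limited residual disease of IGA 2 or more is possible at entry.

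What is at stake is the reading of one published percentage and its confidence interval: some of it may describe what dupilumab had already done.

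**Working it through.** **The plan's own figure.** The only number is the sample size: up to 20 screened so that 16 complete. No power or precision calculation is given, and no figure is attached to this endpoint, so there is nothing to reproduce. (16/0.80 = 20, so the two numbers agree if total loss is taken as 20%; the plan states no rate.) N = 16 completers is used below.

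**Notation.** These quantities are assumptions, because the documents give no BSA distribution:

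- k = completers with BSA below 3% before treatment
- s = those of the k who are still below 3% at Week 16
- t = completers at 3% or more before treatment who are below 3% at Week 16

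**Formulas.**

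- As written: (s + t)/16
- At risk (pre-treatment BSA of 3% or more): t/(16 − k)

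The as-written rate is a weighted average of s/k and t/(16 − k), with weights k/16 and (16 − k)/16. It therefore exceeds the at-risk rate only when s/k > t/(16 − k), and the difference can take either sign.

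**Results with t = 3.** Intervals are exact (Clopper-Pearson) 95%; the plan does not name a method.

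| k | s | As written | At risk | Difference (points) |
|---|---|---|---|---|
| 0 | 0 | 3/16 = 18.75% (4.0 to 45.6) | 3/16 = 18.75% (4.0 to 45.6) | 0 |
| 1 | 1 | 4/16 = 25.00% (7.3 to 52.4) | 3/15 = 20.00% (4.3 to 48.1) | +5.00 |
| 1 | 0 | 3/16 = 18.75% (4.0 to 45.6) | 3/15 = 20.00% (4.3 to 48.1) | −1.25 |
| 2 | 2 | 5/16 = 31.25% (11.0 to 58.7) | 3/14 = 21.43% (4.7 to 50.8) | +9.82 |
| 2 | 1 | 4/16 = 25.00% (7.3 to 52.4) | 3/14 = 21.43% (4.7 to 50.8) | +3.57 |
| 2 | 0 | 3/16 = 18.75% (4.0 to 45.6) | 3/14 = 21.43% (4.7 to 50.8) | −2.68 |

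**Results with no change in anyone (t = 0, s = k).**

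- k = 1: 1/16 = 6.25% (0.2 to 30.2) as written, 0/15 = 0% (0 to 21.8) at risk.
- k = 2: 2/16 = 12.5% (1.6 to 38.3) as written, 0/14 = 0% (0 to 23.2) at risk.

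The second set shows the problem most plainly: a non-zero achievement rate with no change in any subject.

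**The case against.** The strongest reply is that achieving can be read as a transition, which would fit the stated aim. That reading is available, but nothing in either document defines the word so, and inclusion criterion 5 uses the same verb for a state at screening. If a transition is meant, the endpoint should say so.

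Second, other planned output would reveal the issue. Change in BSA is the next secondary outcome, baseline continuous characteristics are to be summarised with minimum and maximum (BSA is not named, but would naturally fall there), and "Individual subject listings will be provided". A minimum baseline BSA of 3% or more would show that the problem is absent. This stands as disclosure. It does not correct the reported proportion or its interval.

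Third, the proportion below 3% at Week 16 is a coherent status measure, and under it a subject who worsens to 3% or more is rightly a non-achiever. This also stands: the negative rows in the table are differences between two definitions, not mistakes. The weakness is in attributing the status to apremilast without knowing how many subjects had it beforehand.

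Fourth, the size is assumed. The title describes recalcitrant moderate-to-severe disease and entrants must be suitable for systemic treatment, so low-BSA entrants are less likely; the intervals for the two definitions also overlap heavily. All true, and the reason the point is minor. Neither description is a BSA floor, however. Nor is the IGA: it is called a global assessment and no text expressly excludes extent, but no grade carries an area threshold.

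**Conclusion.** The concern holds, as a minor point. As written, the endpoint counts an unchanged subject who was already below 3%, and no entry rule prevents such a subject from enrolling. With 16 completers, each one who stays low adds 6.25 points to the reported rate. For one or two low entrants and three true crossings, the difference from the at-risk rate runs from −2.7 to +9.8 points. With no low entrants it is zero.

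The conclusion about the definition rests on the text alone. The size rests on assumed counts. No hypothesis test, sample size or primary result depends on this endpoint.

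**What to change.** Reword the Protocol's secondary outcome i, and add one line to the SAP, along these lines: *proportion of completers with BSA < 3% at Week 16 among those with pre-treatment BSA of 3% or more*, with that denominator stated. Also name which measurement counts as pre-treatment, since the Schedule of Assessments lets baseline fall up to 4 weeks from screening.

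Beside it, report two counts: completers below 3% before treatment, and completers below 3% at Week 16 among all completers. Together they keep worsening visible:

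worsened = pre-treatment count − (all-completer Week 16 count − at-risk numerator)

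For example, 3/14 at risk, 2 low before treatment and 3/16 at Week 16 give 2 − (3 − 3) = 2 worsened. A two-by-two table of pre-treatment against Week 16 status carries the same information. Keeping the present endpoint and adding that table would be a lighter alternative, but the headline proportion would then still include unchanged subjects.

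No new data are needed, because BSA "of involved skin will be measured at Screening, Baseline, and at following visits according to the Schedule of Assessments". The cost is a smaller denominator, of a size not known until enrolment is complete, and a slightly wider interval. At an observed 50%, the exact 95% half-width is 25.3 points at n = 16 (8/16: 24.7 to 75.3), 27.0 at n = 14 (7/14: 23.0 to 77.0) and 28.9 at n = 12 (6/12: 21.1 to 78.9). The change does not substitute for a control arm.
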